**Figure 2. Gantt Chart**

[figure not shown]
	Yr 1				Yr 2				Yr 3				Yr 4			
Activity	Q1	Q2	Q3	Q4	Q1	Q2	Q3	Q4	Q1	Q2	Q3	Q4	Q1	Q2	Q3	Q4
Train Staff																
Obtain IRB Approval																
Finalize Website Specifications and Beta Testing of Website																
Enroll and Randomize to WEB Intervention or Control																
Intensive Intervention and Outcomes Data Collection (6 months)																
Maintenance Intervention (6 months)																
Data Cleaning, Analyses, Manuscript Preparation																

(b) It is useful to specifically relate each experiment to particular hypotheses and/or key questions. Describe the research design, methods, and procedures to be used to accomplish the specific aims of the application.

At VA Boston and VA Birmingham, a total of 185 subjects with COPD will be randomized with an allocation ratio of 1:1 to one of 2 arms: (1) written instructions and education to exercise (usual care) or (2) pedometer and Internet-mediated walking program. Subjects will participate

in the study for a total of up to 13 months, depending on the timing of the C12 in-clinic study visit. The intensive interventional phase will be 6 months followed by a maintenance intervention phase of 6 months and a subsequent 14-day step count collection using a pedometer at 12-months (up to 13 months). Six-minute walk test distance at 6 months will be the primary outcome to assess the efficacy of the Internet-mediated, pedometer-based walking program. Since we are studying the efficacy of a walking intervention, the 6MWT distance is the primary outcome of choice. Secondary outcomes include HRQL, dyspnea, CRP and IL-6 levels, risk of AEs and COPD-related hospitalizations, engagement in PA assessed by daily step count. Additional secondary outcomes include body composition (adiposity) and bone mineral density at baseline and 12 months (in the subset of subjects enrolled at VA Boston only). The study contact timeline and assessments are summarized in Figure 3. Subjects will have an in-clinic assessment at baseline, 3, 6, and 12 months, and a telephone call at 9 months. We anticipate drop-out at 6 months to be at most 40%, resulting in at least 55 subjects who will complete each arm of the study.

**Figure 3.** Protocol Summary. C=Clinic visit, P=Phone call.

**Inclusion Criteria** are:

- a) Male and female subjects, greater than or equal to 40 years of age

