Based on our previous work, medical problems and temporary suspension from the exercise program will be the most common reason for missing outcomes data in both arms. We have designed the testing windows to minimize missing data. At months 3 and 6, testing will be allowed within a window of  $\pm 2$  weeks. At months 9 and 12, testing will be allowed within a window of  $\pm 1$  month, making the total participation time up to 13 months from the baseline in-clinic study visit (C00). Despite our efforts at follow-up, some missing data are expected with multiple testing visits. We will collect the reasons for missing data such as death, COPD exacerbation, medical reasons, or non-medical reasons. We will compare the rate of losses to follow-up at 3, 6, 9, and 12 months among the two arms using the chi-square test of association. We will assess whether any baseline characteristics such as age, FEV1 % predicted, or 6MWT distance, are associated with losses to follow-up using chi-square tests for categorical baseline data and analysis of variance for continuous baseline data. If baseline variables and treatment group are found to be associated with loss to follow-up, then the analysis models will be modified to include the differing baseline variables as covariates to provide unbiased estimates of intervention effects. For subjects who discontinue the study early due to worsening of COPD or due to death, missing outcome data will be imputed using the least favorable data observed prior to discontinuation. Missing data for subjects who miss a visit not related to worsening of COPD will be imputed using last observed data. We will also perform sensitivity analyses using the complete case method, excluding those with no observed outcome at 6 months.

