### **Statistics (power analysis)**

Prior to analyzing the outcomes, we will summarize and compare baseline demographic and clinical variables by treatment group. Any unbalanced characteristics occurring despite randomization will be assessed as potential confounders in multivariate analyses. Analyses will be performed with the SAS statistical software package (9.3, SAS Institute; Cary, NC).

**Primary Aim:** To determine the efficacy of the WEB intervention to increase 6MWT distance.

We focus on 6MWT distance at 6 months since we predict that the greatest difference in 6MWT distance between study arms will occur at month 6, at the end of the interventional phase. We have revised our statistical analysis plan to use 2-way factor analysis or analysis of variance (ANOVA). This approach will assess the effect of intervention versus control on 6MWT distance, using absolute measures of 6MWT distance at baseline and 6 months. Two-way ANOVA will allow us to assess the effect of treatment (intervention versus control), and additionally allow us to assess the interaction between treatment and time (treatment-time) on 6MWT distance. We will use a mixed model (PROC MIXED in SAS) to perform the 2-way ANOVA given its flexibility of modeling the variances and covariances, its robustness in accounting for correlated data (repeated measures data), and its flexibility in handling missing data. Models will have 6MWT distance as the dependent variable, and treatment, time, and treatment-time as independent variables. In this approach, models will also include study site and any unbalanced baseline characteristics as covariates. Primary analyses to determine the effect of WEB on 6MWT distance will use the intention-to-treat approach to include as many randomized subjects as possible in the analyses. Subjects will be considered to be in his/her randomly assigned arm no matter how much he/she participated in it. As a sensitivity analysis, however, we will examine 6MWT distance on a per-protocol basis, where noncompliant subjects ( $\geq 30\%$  of days with no exercise performed on logs) in each treatment arm will be excluded from the analysis.

**Anticipated Results:** We anticipate that subjects in the intervention group will have significantly higher 6MWT distance than subjects in the control group at 6 months.

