**Power Calculation:** This study is powered on our pre-specified primary outcome of 6MWT distance. Our main comparison is 6MWT distance at 6 months between the WEB intervention and control arms. Our power analysis is based on a widely accepted minimum clinically meaningful change in 6MWT distance of 54 meters and the published standard deviation for 6MWT distance of 80-120 meters (90). Our data in a similar Veteran population showed a standard deviation of 102 meters for 6MWT distance. We use a standard deviation of 100 meters in our power calculation. Using the sample size formula for the comparison of the means of 2 independent samples, we calculate that 55 evaluable subjects in each arm at 6 months will allow

[figure not shown]

detection of a difference of at least 54 meters between the WEB and usual care arms with a power of 80% and  $\alpha=0.05$ . We anticipate a maximal drop-out of 40% at 6 months. In order to have 111 evaluable subjects at 6 months, we plan to enroll a total of 185 subjects.

**Secondary Aims:** To estimate the effect of the WEB intervention on (a) HRQL, as measured by the St. George's Respiratory Questionnaire (SGRQ), (b) dyspnea, (c) CRP and IL-6, (d) risk of AEs and COPD-related hospitalizations, (e) engagement in PA as measured by daily step count, (f) body composition and bone mineral density, and (g) pain.

Our statistical analysis plan for the secondary outcomes is similar to that for the primary outcome. We will use 2-way factor analysis or analysis of variance (ANOVA) to assess the effect of intervention versus control on SGRQ-TS, dyspnea score, CRP and IL-6, and daily step count. We will analyze absolute values of the secondary outcomes at baseline and 6 months. Two-way ANOVA will allow us to examine the effect of our intervention, and additionally allow us to assess the interaction between treatment and time (treatment-time) on the secondary outcomes. We will use a mixed model (PROC MIXED in SAS) to perform the 2-way ANOVA. Models will have SGRQ-TS, dyspnea score, CRP and IL-6, or daily step count as the dependent variable, and treatment, time, and treatment-time as independent variables. Models will also include study site and any unbalanced baseline characteristics as covariates.

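### Primary-model covariates other than site are picked by observed imbalance or drop-out tests, which forgoes the precision of pre-specified adjustment for baseline 6MWT and leaves the model and its primary contrast undefined.

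*Combined protocol and SAP*

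**What the plan says.** The primary model (Statistics (power analysis), Primary Aim) is a two-visit mixed model. 6MWT distance at baseline and at 6 months is the response, and treatment, time and their interaction are the fixed terms. Baseline 6MWT is therefore a response, not a covariate. On adjustment: "models will also include study site and any unbalanced baseline characteristics as covariates". Imbalance is to be looked for in a comparison of baseline variables by arm made before outcomes are analysed, and unbalanced variables are to be assessed as possible confounders. No test, threshold or list is given. The secondary outcomes follow the same rule ("Models will also include study site and any unbalanced baseline characteristics as covariates"), as do the models under Additional Analyses. The exacerbation count model also names prior-year events.

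Minimizing Attrition and Handling Missing Data adds a second rule. Baseline variables, with age, FEV1 % predicted and 6MWT distance as examples, are tested for association with loss to follow-up. If they and treatment group are associated with it, "then the analysis models will be modified to include the differing baseline variables as covariates", and the stated purpose is unbiased effect estimates. No significance level is given. The same section imputes missing outcomes with the last observed value, or with the least favorable one after COPD worsening or death.

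On the test itself, the power section says "Our main comparison is 6MWT distance at 6 months between the WEB intervention and control arms". The Primary Aim text mentions both a treatment effect and a treatment-by-time interaction and does not say which is primary.

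**The concern.** In a properly randomized trial any baseline imbalance is due to chance. A rule that adjusts for whatever happens to be unbalanced selects on noise. The benefit of adjustment comes from how strongly a covariate predicts the outcome, and that does not depend on whether the arms differ on it. The strongest candidate is likely to be baseline 6MWT, which every participant provides, yet the plan does not commit to adjusting for it.

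Three things are at stake:

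- Two analysts following the plan could fit different primary models and test different contrasts.
- Precision that would cost almost nothing is given up.
- With up to 40% drop-out expected at 6 months, a reader may take the claim of unbiasedness at face value when it needs an assumption that the plan does not state.

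The two rules can also collide. If the drop-out trigger selects 6MWT distance, the same baseline value would stand on both sides of the primary model.

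**Working it through.** **Inputs from the plan.** The power section states "We use a standard deviation of 100 meters in our power calculation", a difference of 54 m, 80% power, α = 0.05, 55 evaluable per arm (111 in total), 40% drop-out and 185 enrolled. Allocation is 1:1. Sidedness is not stated; two-sided is assumed because it reproduces the plan's n.

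**Assumptions, not in the documents.** Baseline to month-6 correlation ρ of 6MWT: 0.3, 0.5 and 0.7. Equal SD at both visits. A 5% level wherever the plan selects by imbalance.

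**1. The plan's own figure.** n per arm = 2(1.960 + 0.842)² × 100² / 54² = 53.8, so 54. The t-test version gives 54.8, so 55. Power at 55 per arm is Φ(54 / (100√(2/55)) − 1.96) = Φ(2.832 − 1.96) = 80.8% (80.1% by t). Enrolment: 111 / 0.60 = 185. The sample size reproduces and is not in dispute.

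**2. How often chance alone changes the model.** With k independent baseline variables, P(at least one flagged) = 1 − 0.95^k, which is 40%, 64% and 79% for k = 10, 20 and 30. Correlation between the variables would lower these figures.

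**3. Power by contrast, 55 per arm, complete data.** Power = Φ(54 / (σ*√(2/55)) − 1.96), with σ* = 100 for the unadjusted month-6 difference, 100√(2(1−ρ)) for the interaction and 100√(1−ρ²) for ANCOVA on baseline 6MWT.

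| ρ | Month-6 difference, unadjusted | Treatment-by-time interaction | ANCOVA on baseline 6MWT | ANCOVA n per arm for 80% |
|---|---|---|---|---|
| 0.3 | 81% | 67% | 84% | 49 |
| 0.5 | 81% | 81% | 90% | 41 |
| 0.7 | 81% | 95% | 98% | 28 |

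**4. The selection rule.** This was simulated for the month-6 value alone with one covariate, 8,000 trials per setting. The covariate entered only if its baseline t-test gave p < 0.05, which happened in about 5% of runs.

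| Covariate–outcome correlation | Power, test then adjust | Power, always adjust | Type I error, test then adjust |
|---|---|---|---|
| 0.3 | 81.0% | 84.0% | 4.7% |
| 0.5 | 81.6% | 90.2% | 4.4% |
| 0.7 | 82.4% | 97.8% | 3.7% |

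**5. The interaction.** In a simulated two-visit data set of 185 with complete data, the interaction estimate was 54.67 (SE 9.968) both with and without a time-constant covariate. Such a term shifts both visits equally and cancels. With 40% of month-6 values missing, the SE moved only from 11.9 to 11.8.

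**6. The unbiasedness claim.** Simulation with N = 400,000, true effect 54 m, ρ = 0.7 and 40% drop-out. Imputation is simplified to carrying the baseline value forward.

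| Drop-out depends on | Completers, unadjusted | Completers, adjusted for baseline | Carried forward, unadjusted / adjusted |
|---|---|---|---|
| baseline, same in both arms | 54 m | 54 m | 32 / 33 m |
| baseline, opposite direction by arm | 93 m | 54 m | 22 / 22 m |
| month-6 value, both arms | 48 m | 51 m | 35 / 35 m |
| month-6 value, intervention arm only | 80 m | 67 m | 39 / 40 m |

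Adjustment restores 54 m when drop-out depends only on the measured baseline value and arm, and not otherwise. Under carry-forward the covariate makes almost no difference. In the first row the reason is plain: 40% of values carry no treatment effect, and 0.60 × 54 = 32.4 m.

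**The case against.** The defence has real substance. The imbalance check uses baseline data and is placed before outcome analysis, so it is not a search through results. The plan speaks of assessing unbalanced variables as possible confounders, which may mean more than automatic entry, although the later model sentence reads as automatic. The drop-out trigger requires an association with treatment group as well as with baseline variables. These points narrow the problem, but they supply no threshold or list, and the drop-out trigger cannot be applied until follow-up data are in.

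A reader might infer that the rule inflates false positives or leaves the trial underpowered. Neither is supported. With a single covariate the rule was slightly conservative (type I error 3.7% to 4.7%) and kept power at 81–82%, above the planned 80%. Those simulations do not cover choosing among several models after results are seen.

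A reader might also infer that covariate choice swings the primary result whatever is tested, or that the gaps in step 4 are what age or FEV1 would add. For the interaction with complete data, time-constant covariates are inert. Once ANCOVA on baseline 6MWT is in place, a further covariate correlated 0.5 with both visits (assumed) adds little: 90.5% to 93.4% at ρ = 0.5, and 97.8% to 98.3% at ρ = 0.7.

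Finally, it would be too strong to say that adjustment does not remove bias. It does so in the case where its assumption holds.

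**Conclusion.** The point stands as one of specification and efficiency. Apart from site, the primary model's covariates are chosen by data-driven rules without thresholds, and the primary contrast is not named. ANCOVA on baseline 6MWT beats both contrasts at every correlation shown. Against the unadjusted month-6 difference it gains about 3, 10 and 17 percentage points at ρ = 0.3, 0.5 and 0.7 (84.3, 90.5 and 97.8 minus 80.8). Against the interaction it gains about 17, 10 and 2 (minus 66.8, 80.8 and 95.5).

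These sizes rest on the plan's 54 m, SD 100 m and 55 per arm, on complete data, and on correlations that the documents do not give. The selection figures also assume a 5% imbalance test.

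The claim of unbiased estimates should be qualified. It is right only if drop-out depends solely on measured baseline variables and arm, and covariates do not repair carried-forward values. The size of the carry-forward effect is illustrative, because the plan could carry a month-3 value forward where one exists.

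**What to change.** 1. Name the month-6 arm difference in 6MWT as the primary contrast, in line with the power section.
2. Estimate it with pre-specified adjustment for site and baseline 6MWT. Use either ANCOVA on the month-6 value or a two-visit mixed model with a common baseline mean across arms. Do not enter baseline 6MWT as both response and covariate.
3. Optionally add a short list fixed in advance, such as age and FEV1 % predicted, entered so that it acts on the month-6 value (in the mixed model, through covariate-by-time terms).
4. Delete the imbalance comparison and the drop-out tests as selection rules for the primary model. Report further adjustment, including for drop-out predictors, as sensitivity analyses.
5. Replace the statement about unbiasedness with the assumption it needs: drop-out depends only on measured baseline variables and arm.

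The secondary and additional models repeat the imbalance rule and need matching wording. The cost is SAP text and a few degrees of freedom; no new data are needed.

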1) Objective Walking Assessment and Feedback: The Fitbit Zip pedometer used in our research program was selected because it accurately measures step counts in the majority of persons with COPD, is easy to use, and interfaces with the Internet. By connecting the pedometer to a computer with a USB device called a dongle, participants can upload step-count data to the website and view their progress using a variety of detailed graphs.

2) Individualized Step-Count Goals: Specific step-count goals are more effective than setting goals based on total distance or duration walked (62). High target goals improve performance as long as the goals are not so high that the participant believes they are impossible to achieve (63). Sudden and dramatic increases in PA may also increase the risk of injury and adverse cardiac events. WEB uses an automated algorithm to compute gradually incrementing, individualized step-count goals. Goals are based on step-count data uploaded by the participant, accurately reflecting the participant's current level of walking. Goals are not necessarily increasing over time. For example, if a participant is sick, and thus records low step counts for one week, the subsequent week's goal will be lower than the goal for the week the participant was sick.

3) Motivational Messages and Educational Tips: Persons who are sedentary or who have chronic disease face general and disease-specific barriers to starting and maintaining a walking program. Specific strategies and behavioral techniques for overcoming these barriers are addressed as part of the motivational messaging component of WEB. Education about disease management, the benefits of PA, and behavior change is also provided online, and some messages are tailored to smokers or oxygen users for more targeted and relevant information. These features promote exercise self-efficacy and confidence, and encourage compliance. Users view these materials on their website study page.

4) Online Community: An online community within the WEB website maintains social support by allowing participants to share ideas about promoting PA. [name] et al. demonstrated that subjects with access to an online community remained engaged in the intervention for a longer time and were less likely to drop out than those without access to an online community (64). Participants who posted more frequently on the online community increased their step counts more than those who posted less frequently (64).

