### Assessment of Treatment Fidelity

To promote treatment fidelity in both groups, study staff will review instructions to slowly and steadily increase walking and exercise with participants every 3 months (98). To measure treatment fidelity in both groups, subjects will complete daily exercise logs (98). The exercise log is intentionally simple to minimize its potential influence to be part of the intervention (Appendix 2). Subjects circle a yes/no response to three questions about whether exercise was performed that day. Subjects will return the logs by mail to study staff every month, and review them in person every 3 months. Compliance with treatment in both arms will be defined as having >70% of days (~5 out of 7 days/week) with exercise. We propose an intention-to-treat analysis since the reasons for noncompliance may be related to COPD severity. Thus, all subjects will be analyzed and not excluded based on compliance. As a sensitivity analysis, however, we will examine 6MWT distance and secondary outcomes on a per-protocol basis, where noncompliant subjects ( $\geq 30\%$  of days with no exercise performed on logs) from each treatment arm will be excluded from the analysis (Table 2).

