Total number of AEs and COPD-related hospitalizations will be summed over the 12-month study period. Independence of individual AEs will be assured by considering subjects to have experienced a new AE only if they had been off of oral steroids and antibiotics for at least 14 days following the previous AE (86). Given the count data and expected Poisson distribution of number of AEs and hospitalizations, negative binomial regression models (PROC GENMOD) will be used to calculate risk ratios for AE and COPD-related hospitalizations (86). The

multivariate regression model will include number of AEs (or hospitalizations) as the dependent variable, treatment group as the main predictor, as well as study site, number of AEs (or hospitalizations) in the year prior to enrollment, and any unbalanced baseline characteristics.

**Body Composition by DXA Scan:** Body composition and regional fat analysis will be performed at the baseline study visit and the 12-month study visit using standard software available from the manufacturer. For regional fat measurements, the left and right arm cuts pass through the shoulder joints and as close to the body as possible. The leg cuts separate the hands and forearms from the legs, starting with a diagonal cut through the femoral necks. The midline separates the right and left legs. The images obtained from one of our subjects demonstrate the standard cuts that define the arms, legs, and trunk (see figure to the left). These data can be also be used to calculate a waist-hip ratio (i.e., ratio of

central fat to hip fat) in a standardized fashion using the same landmarks as illustrated by the regions defined on the soft-tissue image. The DXA software can be used to define standard waist and hip regions that will allow comparability of these measurements throughout the study. The lower boundary of the central or waist region, which is also referred to as the android region (A, see figure), is the cut through the pelvis at the level of the iliac crests. The upper boundary of the android region extends upwards to 20% of the distance between the pelvis and the top of the shoulders and the lateral boundaries are the arm cuts. The upper boundary of the gynoid region of interest (G, see figure) is the region below the pelvis cut that extends downward from 1.5 times the height of the android region. Lateral boundaries of the gynoid region are the outer leg cuts.

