**Power Calculations:** A sample size of 111 evaluable subjects at 6 months determined by the primary outcome of 6MWT distance will also allow detection of significant differences in the secondary outcomes. Using the sample size formula for the comparison of the means of 2 independent samples, we can detect an effect size of 0.55 SD units with 80% power and  $\alpha=0.05$ . Using the SD's obtained from our cross-sectional observational study, we can detect a change of at least 10 units in SGRQ-TS, 1.8 mg/L in CRP level, and 0.59 pg/mL in IL-6 level. In addition, as an estimate for anticipated differences between arms, we examined the mean 6MWT distance, SGRQ-TS, CRP, and IL-6 levels in those who walked above and in those who walked below the median daily step count in our observational data. We observed a difference of 1.27 pg/mL in IL-6 in those who walked above and in those who walked below the median daily step count, values greater than our detectable difference suggesting sufficient power. We found a difference of 7 units in SGRQ-TS and 0.96 mg/L in CRP. While these preliminary observed estimates of difference in SGRQ-TS and CRP are slightly smaller than our calculated detectable estimates, we anticipate there will be sufficient power to detect differences in these secondary outcomes when the analyzed groups are differentiated by the WEB intervention, since our power calculations based on groups dichotomized at the median step count are conservative. In calculating power for detecting differences in risk of AEs, we expect to observe 106 AEs in the 111 subjects completing a 12-month follow-up period based on our preliminary data. Given this rate and using the POISS\_SS macro of E. Bergstralh (a Poisson power calculator), we will be able to detect a rate ratio of at least 1.70 with 80% power and 1.85 with 90% power. Again, to estimate anticipated observed differences between treatment arms, we examined the number of AEs in those who walked above and in those who walked below the median daily step count in our observational data. One hundred thirty-six AEs were observed in those who walked below the median daily step count and 76 AEs were observed in those who walked above the median daily step count, an observed rate ratio of 1.79, indicating adequate power.

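### The exacerbation and hospitalization model has no follow-up-time offset, so unequal drop-out would bias its ratio, and its power statement treats the 111 evaluable at 6 months as 12-month completers

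*Combined protocol and SAP*

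**What the plan says.** Under Statistics (power analysis), Secondary Aims: "Total number of AEs and COPD-related hospitalizations will be summed over the 12-month study period". The "multivariate regression model will include number of AEs (or hospitalizations) as the dependent variable, treatment group as the main predictor", with study site, the prior-year count and any unbalanced baseline characteristics as the other terms. Neither that paragraph nor any other part of the document mentions an offset, person-time or a rate denominator.

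Minimizing Attrition and Handling Missing Data gives two general rules. After discontinuation for worsening COPD or death, the least favorable earlier value is used. Otherwise, "Missing data for subjects who miss a visit not related to worsening of COPD will be imputed using last observed data". The same section plans to compare loss between arms and gives one remedy: "If baseline variables and treatment group are found to be associated with loss to follow-up", the differing baseline variables become covariates.

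Assessment of Treatment Fidelity proposes intention-to-treat: "Thus, all subjects will be analyzed and not excluded based on compliance".

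The primary Power Calculation states: "In order to have 111 evaluable subjects at 6 months, we plan to enroll a total of 185 subjects". The Power Calculations for the secondary outcomes begin with the same 111 at 6 months and later say "we expect to observe 106 AEs in the 111 subjects completing a 12-month follow-up period". From this they derive detectable rate ratios of 1.70 (80% power) and 1.85 (90% power) with a Poisson calculator.

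**The concern.** Without person-time, the model estimates a ratio of mean counts. That equals a rate ratio, which is what the power section refers to, only if mean follow-up is the same in both arms. The plan expects substantial loss and foresees that it may be related to treatment, but baseline covariates do not restore lost time at risk.

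The missing-data rules suit a score measured at visits. For a running total, the last observed value and the least favorable value are both the count already reached. A participant who leaves at month 2 is then treated as event-free for ten months.

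The direction of any bias is unknown. Background and Significance, under Online Community, cites a study in which "subjects with access to an online community remained engaged in the intervention for a longer time and were less likely to drop out". Only the WEB arm has such a community, but that study did not compare against usual care, so it is only suggestive. If control loses more people, the bias would hide a benefit. If WEB loses more, it would create one.

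Separately, the AE power rests on 111 people followed for 12 months, a number derived only for month 6.

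**Working it through.** **Inputs from the documents.** 185 randomized 1:1; at most 40% drop-out at 6 months; 106 AEs in 111 people over 12 months, or 106/111 = 0.955 per person-year; 0–4% loss at 12 months in the team's other studies; α = 0.05 (taken as two-sided). **Not given, so assumed:** drop-out by arm, loss after month 6, and dispersion k.

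**The plan's own figures.** 185 × (1 − 0.40) = 111, reproduced as a 6-month number. For 106 events split 1:1, the detectable ratio is exp[2(1.960 + 0.842)/√106] = 1.72 at 80% power and 1.88 at 90%, close to the stated 1.70 and 1.85. (Using 111 events gives exactly 1.70 and 1.85. This small gap is not part of the point.)

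**Bias without an offset, true ratio 1.** If a proportion d of an arm leaves after 3 months on average, mean exposure is (1 − d) + 0.25d years. The expected ratio is the WEB exposure divided by the control exposure.

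| Loss WEB / control | Calculation | Ratio |
|---|---|---|
| equal | – | 1.00 |
| 4% / 0% | 0.97/1 | 0.97 |
| 25% / 15% | 0.8125/0.8875 | 0.92 |
| 45% / 35% | 0.6625/0.7375 | 0.90 |
| 50% / 30% | 0.625/0.775 | 0.81 |
| 35% / 45% | 0.7375/0.6625 | 1.11 |
| 30% / 50% | 0.775/0.625 | 1.24 |

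A constant drop-out hazard over 12 months gives somewhat larger shifts. With h = −ln(1 − d)/0.5 and exposure (1 − (1 − d)²)/h, where d is the 6-month loss, 45%/35% gives 0.583/0.670 = 0.87 and 50%/30% gives 0.541/0.715 = 0.76.

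**False-positive rate (simulation, 185 randomized, 0.955 AEs per year, two-sided 5%).**
- k = 0.5, drop-out uniform over months 0–6, 1,500 runs. Without offset: 4.6% (40/40), 7.9% (45/35), 8.6% (35/45), 15.8% (50/30), 16.9% (30/50). With offset: 4.7–6.7%, mean ratio 1.00–1.01.
- k = 0.7, constant hazard, 600 runs. Without offset: 5.2% (40/40), 18.5% (50/30), 19.7% (30/50). With offset: 5.5–7.5%, ratio 0.99–1.01.

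**The 111.** With 40% lost by month 6, having 111 complete 12 months requires no loss afterwards. Alternatively, at constant hazard, loss by month 6 would have to be only 1 − √0.6 = 22.5%. If a further 10% or 20% of the 111 leave, about 100 or 89 complete, expected AEs fall to 95 or 85, and the 80%-power ratio rises from 1.72 to 1.77 or 1.84.

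**Power with the offset and all 185, ratio 1.70.** At 40% loss per 6 months, h = −ln(0.6)/0.5 = 1.0217. Person-years = 185 × (1 − 0.36)/1.0217 = 115.9, and AEs = 115.9 × 0.955 = 110.7. Splitting the events 1.7:1 gives 69.7 and 41.0, and Var(log ratio) = 1/69.7 + 1/41.0 + 2k/92.5.
- k = 0: 77% (80% using the null variance)
- k = 0.5: 66% (64% if information is summed over individual follow-up times)
- k = 1.0: 58% (54% likewise)

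At 4% loss over 12 months there are 181.3 person-years and 173.1 AEs, and power is about 92%, 80% and 69%. None of these figures allows for adjustment for prior AEs.

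**The case against.** **The bias needs two conditions:** truncated counts must enter the model as totals, and loss must differ by arm. The only text describing the AE population speaks of completers, and the intention-to-treat sentence concerns exercise compliance rather than loss to follow-up. This is fair. With completers only, the exposure bias largely disappears, but observed events are discarded and selection takes its place. The plan does not say which set applies.

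**Nothing quantitative points to differential loss.** Table 2 expects health reasons, the main cause of missing data, to act equally in both arms. The 40% is a ceiling chosen to size the walk test, and the team reports 0–4% loss elsewhere. This stands: every ratio other than 1.00 is a scenario, and at 4% versus 0% the shift is only 3%.

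**Events can be recovered** through the month-9 call, participants' own calls and record review. This holds for a missed visit. Record review is prompted by patient report, however, and nothing says it runs to month 12 for permanent drop-outs.

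**An offset assumes a constant rate and non-informative drop-out.** Leaving because COPD worsens is informative, and the simulations drew drop-out independently of events, so recovery of 1.00 is by construction. This limit remains, but the model without an offset shares it and has the exposure bias as well.

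**No power shortfall is shown.** Correct: the direction against 80% depends on retention and dispersion. The plan does expect Poisson counts, so the calculator matches that expectation, though not the negative binomial analysis.

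**Conclusion.** The concern holds and should be addressed. The model as written has no protection against unequal follow-up, the analysis set for counts is not named, and the imputation rules leave truncated totals in place. If all randomized participants are analyzed with average loss near the 40% ceiling, a 10-point difference between arms moves a null ratio by roughly 10–13%. A 20-point difference moves it by roughly 19–32%, with a false-positive rate of about 16–20%. Equal loss gives no exposure bias, and loss in the 0–4% range gives little. These sizes rest on assumed arm-specific drop-out, drop-out timing and dispersion. The relabeling of the 6-month 111 as 12-month completers is plain from the text, but its effect on power could go either way. Only a secondary outcome is affected; the 6MWT sample size is not.

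**What to change.** In the Secondary Aims analysis of AEs and hospitalizations:

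1. Add log(time from randomization to last AE ascertainment) as an offset in PROC GENMOD, and state that this assumes drop-out is non-informative given the covariates.
2. Name the analysis set: all randomized participants with any follow-up.
3. Exempt event counts from the last-observed and least-favorable rules.
4. In the secondary Power Calculations, correct the description of the 111, state a 12-month retention assumption, and restate AE power from expected person-years with a stated allowance for overdispersion.

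The cost is SAP wording, one model option and a last-ascertainment date per participant, which the scheduled visits and calls supply. No extra patients are needed: even at 40% loss per 6 months, the 185 randomized give about 111 expected AEs against the planned 106.
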